**7.3.4.1. PHYSICIAN GLOBAL IMPRESSION OF SEVERITY (PhGIS-AAP)**

Please mark an “X” in the box (☐) that best describes the severity of the subject’s patchy alopecia areata right now.

Overall, how severe is the subject’s patchy alopecia areata right now?

- Mild
- Moderate
- Severe
- Very Severe
- Extremely Severe

**7.3.4.2. PHYSICIAN GLOBAL IMPRESSION OF SEVERITY (PhGIS-AT/AU)**

Please mark an “X” in the box (☐) that best describes the severity of the subject’s alopecia totalis or alopecia universalis right now.

Overall, how severe is the subject’s alopecia totalis or alopecia universalis right now?

- Mild
- Moderate
- Severe
- Very Severe
- Extremely Severe

**7.3.5. Physician Global Impression of Change (PhGIC)**

The investigator will assess the global impression of change in the subject’s hair loss (AA, AT or AU) at Week 24 (Visit 9) using the PhGIC detailed below.

Compared to the subject’s hair loss at Baseline [prior to study medication initiation], the subject’s AA, AT or AU is (Please mark an “X” in the box ☐):

- 1=Very much improved since the initiation of treatment;
- 2=Much improved;
- 3=Minimally improved;
- 4=No change from baseline (the initiation of treatment);
- 5=Minimally worse;
- 6= Much worse;
- 7=Very much worse since the initiation of treatment.

### 7.3.6. Hair Quality Assessments

Hair quality will be assessed by the investigator using the hair pull test including the presence of exclamation point hairs at Baseline and then monthly during the study. For subjects with AU or AT, the hair pull test will not be conducted.

#### 7.3.6.1. Hair Pull Test

The hair pull test is performed at the edge of the alopecic (target) patch as follows:

- Pinch 25 to 50 hairs between non-gloved thumb and forefinger and exert slow, gentle traction while sliding fingers up.
- Resulting extracted hairs should be examined with magnification and counted.
  - Normal: 1 to 2 hairs dislodged
  - Abnormal: >2 hairs dislodged
  - Broken hairs (structural disorder)
  - Broken-off hair at the borders of an alopecic patch that are easily removable (in alopecia areata) (exclamation point hair)

### 7.3.7. Severity Alopecia Tool (SALT) Score

The SALT score is a measurement of the amount of terminal scalp hair loss. The investigator will assess the SALT score using an iPad provided by Aclaris at screening, Baseline, Day 15 (Visit 3) and at the visits detailed in Schedule of Assessments (Table 3). The SALT score must be determined prior to the ALODEX score. At Baseline (Visit 2), the SALT score must be determined prior to randomization and the score must be within 30% to 100% total scalp hair loss for the subject to receive study treatment. Equipment, supplies, training and the detailed Reference Guide will be provided to the investigational site prior to the initiation of subject enrollment.

### 7.3.8. Alopecia Density and Extent Score (ALODEX)

The ALODEX score is a measurement of the amount of terminal scalp hair loss. The investigator will calculate the ALODEX score using the iPad provided by Aclaris at Screening, Baseline, Day 15 (Visit 3), and at the visits detailed in Schedule of Assessments (Table 3). The ALODEX score must be determined after the SALT score. At Baseline (Visit 2), the ALODEX score must be determined prior to randomization. Equipment, supplies, training and the detailed Reference Guide will be provided to the investigational site prior to the initiation of subject enrollment.

### 7.3.9. Vellus and Indeterminate Hair Assessment

The investigator will assess if vellus and indeterminate hair are present on the scalp by completing the question:

Is vellus hair present in the areas of hair loss? Y, N

Is indeterminate hair present in the areas of hair loss? Y, N

Hair types are characterized by the diameter and length of the hair shafts. Vellus hair is soft, hypopigmented, unmedullated and less than 0.03 mm in diameter and less than 1 cm in length.

Terminal hair is longer, coarser, often medullated, pigmented, and  $> 0.06$  mm in diameter and  $> 1$  cm in length. Indeterminate hairs are intermediate in size between terminal and vellus hairs ( $>0.03$  mm and  $<0.06$  mm in diameter).

#### **7.4. Photographic Assessment**

A qualified investigational staff member will take standardized photographs of the scalp at Baseline and then monthly during the study. The photographs are to document the Baseline hair loss and hair growth during treatment. Photography is a required element of the study procedures and is not considered optional. During initial study discussion as part of consent procedures, site staff should ensure that subjects are fully aware of this aspect of study participation.

Subjects should be instructed to maintain the same hairstyle and color throughout the study. It is important for the staff member to clip the hair as detailed in the instructions provided, so the areas of hair loss and possible regrowth are visible at baseline and monthly throughout the study. Equipment, supplies, training and detailed instructions for obtaining and managing photographs and clipping the hair will be provided to the investigational center prior to the initiation of subject enrollment.

## **8. ASSESSMENT OF SAFETY**

### **8.1. Safety Parameters**

Safety will be assessed throughout the study by the investigator or a designated and appropriately trained staff member.

#### **8.1.1. Demographic/Medical History/ Alopecia Areata History**

During the screening visit, the investigator or designee will interview each subject to obtain demographic information including date of birth, sex at birth, Fitzpatrick skin type, race and, if appropriate, ethnicity. The investigator or designee will interview each subject to obtain medical history information related to all medical conditions, surgeries and disease states that, at screening: are ongoing, require concomitant therapy or are, in the opinion of the investigator, relevant to the subject's study participation. In addition, the medical history of women who are not of childbearing potential should reflect the reason e.g. post-menopausal for 1 year or greater, bilateral tubal ligation, or hysterectomy. The investigator or designee will also obtain an alopecia history at screening ([Appendix 1](#)). The subject's alopecia history is captured on a separate source document and eCRF and is not documented as part of the subject's general medical history.

#### **8.1.2. Vital Signs**

Vital signs will be measured at each visit during the study. The following items will be measured:

- Body temperature
- Pulse rate
- Respiration rate
- Blood pressure (systolic and diastolic) after the subject sits quietly for at least 5 minutes
- Height (at Visit 1 only)
- Weight (at Visit 1 only)

Any measure that is, in the opinion of the investigator, abnormal AND clinically significant (CS) must be recorded as medical history if found prior to the first study medication administration, or as an AE if found after the first dose of study medication.

A systolic blood pressure >140mm Hg or a diastolic blood pressure >90 mmHg is considered abnormal and therefore must be defined as CS or not clinically significant (NCS) in the eCRF. A weight >300 lbs. is considered abnormal and therefore must be defined as CS or NCS in the eCRF.

#### **8.1.3. Physical Examination**

The investigator or designee will perform a physical examination for all body systems at Screening (Visit 1) and end of treatment Week 24 (Visit 9). The skin assessment portion of the Physical Examination does not require documentation of alopecia as an abnormality since it is

the indication of interest for this study and required for participation. In the absence of any other abnormalities, skin should be considered “Normal” for these subjects.

#### 8.1.4. Electrocardiogram (ECG)

Standard 12-lead ECGs will be performed by a qualified staff member at Screening (Visit 1), Visit 3, and Visit 9 as detailed in Schedule of Assessments (Table 3). The ECGs must be obtained using a standard 12-lead ECG with a 10mm/mV amplitude, at 25mm/sec and a 5 to 10 second duration. To ensure a steady heart rate the subject must rest quietly in the supine position for at least 5 minutes prior to performing the ECG.

A central lab, eResearchTechnology, Inc. (ERT), will provide ECG equipment, supplies and site training. In addition, ERT will process ECGs received by the sites and report results via a secure study portal. The ECG results will be interpreted by a qualified health professional (evaluator) and the interpretation reported on a separate report which includes a copy of the tracing. The evaluator will interpret the results of every ECG and define the ECG as “normal” or “abnormal”. Variations such as minor ST changes (i.e., <0.5mm depression) and early re-polarization are considered normal.

The investigator must review the evaluator’s interpretation of each subject’s screening ECG prior to Baseline (Visit 2). The investigator will review the evaluator’s interpretation of all ECG reports in a timely manner and comment on the clinical relevance of any result that is defined by the evaluator as abnormal.

Any abnormalities that are, in the opinion of the investigator, clinically significant, must be reported as medical history if found prior to the start of the first dose of study medication or as an AE if found after the start of the first dose of study medication (see Section 8.2 ).

#### 8.1.5. Clinical Laboratory Assessments

A qualified staff member will collect non-fasting samples for clinical laboratory analysis at the visits detailed in Schedule of Assessments (Table 3). Samples will be sent to a central laboratory for analysis. Refer to the study specific laboratory manual for handling and shipping instructions. The following tests will be conducted:

##### Chemistry Panel

Albumin  
Alkaline phosphatase  
Alanine aminotransferase (ALT)  
Aspartate aminotransferase (AST)  
Blood urea nitrogen (BUN)  
Bicarbonate  
Calcium  
Chloride  
Creatinine  
Glucose  
Lactate dehydrogenase (LDH)

##### Complete Blood Count

Hematocrit  
Hemoglobin  
Platelet count  
Red blood cell morphology  
Red blood cell count  
White blood cell count  
White blood cell differential  
% & absolute  
Basophils  
Eosinophils  
Lymphocytes

Phosphorus	Monocytes
Potassium	Neutrophils
Sodium	
Total bilirubin	Urinalysis
Total protein	
Uric acid	Screening Only
	Virology (HepB, HCV, HIV)
Total cholesterol, LDL, HDL,	Quantiferon Gold
Triglycerides	Total Iron Binding Capacity (TIBC)
Urine Pregnancy Test for WOCBP (Screening, Baseline, at the visits detailed in Schedule of Assessments (Table 3).	Serum iron
	Serum Ferritin
	T3/ Free T4, TSH
	Serum pregnancy

The following clinical laboratory tests: TIBC, serum iron, serum ferritin, T3/ Free T4, TSH are drawn at screening to rule out any underlying conditions that could be causing alopecia. Total cholesterol, LDL, HDL and Triglycerides will be assessed at all visits. The results of the clinical laboratory tests will be reported on the central laboratory's standard reports. The investigator must note NCS or CS to define the clinical relevance of any result that is outside the normal range for the laboratory. The investigator must date and initial every laboratory report.

The investigator or subinvestigator must review all the Screening (Visit 1) laboratory test results against the study entry criteria and the Study Medication Interruption Criteria [Table 2](#) for each subject prior to Baseline (Visit 2). Subjects with Screening laboratory values meeting the Study Medication Interruption Criteria found in [Table 2](#) must have repeat laboratory testing performed with results meeting the minimum criteria for resumption in order to initiate treatment at Baseline (Visit 2).

The investigator must report all laboratory results that are BOTH outside the normal range for the laboratory AND, in the opinion of the investigator, CS as medical history if found prior to the first study medication treatment or as an AE if found after the first study medication treatment begins. The investigator must review all laboratory reports in a timely manner.

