**Table 3: Schedule of Assessments**

	Screening	Baseline	Treatment							Post-Treatment
	Visit 1	Visit 2	Visit 3 	Visit 4	Visit 5	Visit 6	Visit 7	Visit 8	Visit 9 (ET)	Visit 10 
Week		0	2	4	8	12	16	20	24	28
Treatment Day	-30 to 0	1	15	29	57	85	113	141	169	197
Treatment Window(days)	N/A	N/A	± 3	± 3	± 3	± 3	± 3	± 3	± 3	± 3
Informed consent 	X									
Inclusion/exclusion criteria	X	X								
Physical exam 	X								X	
Demographics & medical history	X									
Alopecia Areata History	X									
Vital signs 	X	X	X	X	X	X	X	X	X	X
Clinical CBC, Chemistry, Virology, Serum Pregnancy, Urinalysis 	X	X	X	X	X	X	X	X	X	X
Blood for PK (Select Sites Only) 		X (Pre-dose)		X		X			X	
Urine pregnancy test 	X	X		X	X	X	X	X	X	X
ECG	X		X						X	
Subject	Target Patch identification (Patchy AA Subjects Only)	X								
	Alopecia Scalp Appearance Assessment (ASAA-AAP: SR or ASAA-AT/AU: SR) 		X	X			X		X	X
	Alopecia Facial Hair Appearance Assessment (AFHA: SR)		X	X			X		X	X
	Subject Global Impression of Severity (SGIS-AAP or SGIS-AT/AU)		X	X			X		X	X
	Alopecia Impact Assessment (AIA): Subject Rating		X	X			X		X	X

		Screening	Baseline	Treatment						Post-Treatment	
		Visit 1	Visit 2	Visit 3 	Visit 4	Visit 5	Visit 6	Visit 7	Visit 8	Visit 9 (ET)	Visit 10 
Week			0	2	4	8	12	16	20	24	28
Treatment Day		-30 to 0	1	15	29	57	85	113	141	169	197
Treatment Window(days)		N/A	N/A	± 3	± 3	± 3	± 3	± 3	± 3	± 3	± 3
	Subject Global Impression of Change (SGIC)									X	
	Subject Global Impression Treatment Satisfaction (SGITS-AAP or SGITS-AT/AU) 						X			X	X
	Subject Global Satisfaction with Hair Quality (SGSHQ-AAP or SGSHQ-AT/AU)		X	X			X			X	X
	DLQI 		X	X			X			X	X
Investigator	Alopecia Scalp Appearance Assessment (ASAA: -AAP:CR of ASAA-AT/AU:CR) 		X	X			X			X	X
	Alopecia Facial Hair Appearance Assessment (AFHA: CR)		X	X			X			X	X
	Non-Scalp Hair Loss Assessment (NSHA)		X	X			X			X	X
	Physician Global Impression of Severity (PhGIS-AAP or PHGIS-AT/AU)		X	X			X			X	X
	Physician Global Impression of Change (PhGIC)									X	
	Hair Quality Assessment (Patchy AA Subjects Only)		X				X			X	X

	Screening	Baseline	Treatment							Post-Treatment
	Visit 1	Visit 2	Visit 3 	Visit 4	Visit 5	Visit 6	Visit 7	Visit 8	Visit 9 (ET)	Visit 10 

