### **8.2.1. Definition of Adverse Events**

#### **8.2.1.1. Adverse Event (AE)**

An AE is the development of an undesirable medical condition or the deterioration of a pre-existing medical condition following or during exposure to a pharmaceutical product, whether or not considered casually related to the product.

The investigator should, when certain, report a diagnosis rather than the signs, symptoms or clinically significant abnormal laboratory values associated with the AE. Otherwise, signs, symptoms or abnormal laboratory values may be used to describe the AE.

Every new episode or clinically significant worsening of a chronic condition (e.g., headaches, seasonal allergies, depression, or hypertension) should be reported as a separate AE, even if the condition is reported in the subject's medical history. Hair growth in unexpected areas, such as facial hair in women, should be reported as an adverse event.

Any CS abnormality discovered prior to the first study medication treatment should be reported as medical history, not as an AE.

All AEs that occur after any subject has been enrolled, before treatment, during treatment, or within 30 days following the cessation of treatment, whether or not they are related to the study, must be recorded in the subject's source documents and in the Aclaris' electronic case report form (eCRF). Changes to a subject's medical condition that occur between signing an ICF and beginning treatment should be captured in the medical history.

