### Treatment-Emergent Adverse Event (TEAE)

Any recorded AE that occurs on or after the initiation of study medication and within 30 days after the date of Visit 9 or after the date of last dose of study medication will be considered treatment-emergent.

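### Clinically significant laboratory results are filed as medical history or AE by when they are found, so an abnormality in the Visit 2 pre-dose sample can serve as baseline and also be counted as a treatment-emergent event

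*Protocol*

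**What the plan says.** **Filing by discovery.** Protocol 8.1.5 sends a clinically significant (CS) out-of-range result to one of two places: "as medical history if found prior to the first study medication treatment", or "as an AE if found after the first study medication treatment begins". Section 8.2.1.1 repeats the test: "Any CS abnormality discovered prior to the first study medication treatment should be reported as medical history, not as an AE". Neither sentence mentions when the sample was drawn.

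**Filing by occurrence.** Section 8.2.1.1 also defines an AE as something that develops or worsens during or after exposure to the product. It adds that changes in a subject's condition "that occur between signing an ICF and beginning treatment should be captured in the medical history". The SAP repeats the AE definition.

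**The schedule.** Table 3 marks the row "Clinical CBC, Chemistry, Virology, Serum Pregnancy, Urinalysis" at Visit 2 (Day 1), the visit at which medication is first dispensed. Section 8.1.5 states: "Samples will be sent to a central laboratory for analysis". It requires review before Baseline for the Screening results only.

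**The SAP.** Section 4.3.6 starts its TEAE definition with "Any recorded AE that occurs on or after the initiation of study medication". Section 6.3.1 keeps AEs that start before the first dose out of the TEAE tables. Section 4.3.6 defines Day 1 as a date and takes as baseline the most recent available value before dosing. Section 4.3.7 admits every study day through Day 1 to the baseline window.

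**The concern.** A blood sample drawn before any study drug cannot show an effect of that drug. Under the discovery rule, though, its filing depends on how quickly the central laboratory reports. If the Visit 2 report arrives after the first dose, a literal reading of 8.1.5 makes a pre-dose abnormality an AE. A site that follows the occurrence sentence would file the same result as medical history. Both sites would be following the protocol.

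At stake is the TEAE count in a trial whose primary objective includes the safety of three doses against placebo. One result could be the subject's laboratory baseline and also appear as a treatment-emergent event.

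**Working it through.** No figure in the plan needs reproducing. The check follows one new CS abnormality in the Visit 2 safety sample through the rules.

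**Can the result be found after dosing starts?** Yes.
- The sample leaves the site for a central laboratory; turnaround is not stated.
- The protocol does say when a Visit 2 result must be known first. The urine pregnancy test (8.1.6) and SALT score (7.3.7) must precede randomization. No such condition is set for the Visit 2 bloods.
- Section 3.4.1.1 has the investigator act on receipt of the central laboratory report, which implies a delay after the visit.

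**Are other safety measures exposed?** Sections 8.1.2 and 8.1.4 use the same *found* wording. Vital signs are known at the visit. The only pre-dose ECG is at Screening, and its interpretation must be reviewed before Baseline. The delay therefore arises for laboratory results.

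**Where does the result end up when it is received after the first dose?**

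| Rule the site follows | First dose | Onset date entered | Outcome |
|---|---|---|---|
| Occurrence (8.2.1.1) | any | none | Medical history, no AE |
| Discovery (8.1.5) | same day as draw | collection date = Day 1 | Not before Day 1 by date: TEAE |
| Discovery (8.1.5) | same day as draw | report date, Day 1 or later | TEAE |
| Discovery (8.1.5) | later day | collection date | Before first dose: listed, not in TEAE tables |
| Discovery (8.1.5) | later day | report date | TEAE |

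Neither document says whether a laboratory AE takes the collection date or the report date as onset. The same-day rows assume comparison by date, since Day 1 carries no time. In every TEAE row the same value is also the baseline under SAP 4.3.6 and 4.3.7.

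**Size.**
- Subjects per arm: 95/4 = 23.75, about 24.
- One misfiled subject with no other TEAE adds 1/24 = 0.042 to that arm's any-TEAE rate, about 4 percentage points. A subject who has another TEAE adds nothing to that rate.
- The documents give no rate of new CS results at Visit 2. Purely as an assumption, 1% to 5% of 95 is 0.95 to 4.75, about 1 to 5 subjects study-wide.
- Let m be the chance of a misfiled event, equal in every arm and independent of other TEAEs. A true rate p becomes p + m(1 − p). Take assumed true rates of 30% and 20% (ratio 1.50, difference 10 points).
  - With m = 5%: 0.30 + 0.05 × 0.70 = 0.335 and 0.20 + 0.05 × 0.80 = 0.240, so the ratio is 1.40 and the difference 9.5 points.
  - With m = 1%: 0.307 and 0.208, so the ratio is 1.48 and the difference 9.9 points.

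**The case against.** The strongest reply is that the protocol already holds the right principle. A pre-dose result does not meet the AE definition, and the occurrence sentence sends it to medical history. An investigator who reads 8.2.1.1 as a whole may well file it correctly. A reader might infer that every such Visit 2 abnormality becomes a TEAE. The documents do not support that: the outcome depends on which rule the site follows, when the first dose is taken and which onset date is entered. The SAP defines TEAEs by occurrence, and one of the discovery-rule paths above ends in exclusion.

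Three further replies stand.
- The affected group is narrow. Screening laboratory results are reviewed before Baseline, exclusion criterion 13 removes subjects with disqualifying abnormalities, and an abnormality already known from Screening is already medical history. What remains is a CS finding that is new between Screening and Day 1.
- The SAP laboratory tables are safe. A treatment-emergent laboratory abnormality is a post-baseline value, so the baseline sample itself cannot qualify.
- AE summaries are descriptive, and the chi-square test on overall AE incidence was dropped in Version 5.0.

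These limit the size of the fault but do not remove it. Section 8.1.5 is the section written for laboratory results, its instruction is explicit, and it cannot be obeyed together with the occurrence sentence. Section 8.2.1.1 is itself mixed, since it contains both tests.

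**Conclusion.** Wrong as written, with small impact. The discovery rule in 8.1.5 and 8.2.1.1 conflicts with the protocol's own AE definition and occurrence sentence. Through same-day dosing it can place one value in both the SAP baseline and the TEAE tables.

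This rests on five conditions: the Visit 2 safety sample is drawn before the first dose (implied by its use as baseline, but only the PK row of Table 3 carries a pre-dose label); the result returns after dosing starts; the site applies the discovery rule; the finding is CS and new since Screening; and either dosing starts on the day of the draw or the report date is entered as onset.

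A reader might also infer a bias for or against a particular dose. The documents do not support that, because the rule is the same in every blinded arm. It can add events to all arms, including placebo, and draw ratios slightly toward 1. No planned hypothesis test is affected. The rate of such findings is unknown, so only the per-subject effect of about 4 points can be given with confidence.

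**What to change.** - **Protocol 8.1.5 and 8.2.1.1:** replace the test of when a CS laboratory abnormality was found or discovered with whether the sample was collected before or after the first dose. This brings the discovery sentences into line with the AE definition and the occurrence sentence.
- **Protocol Table 3 and 8.1.5:** state that the Visit 2 safety sample is taken before the first dose, and that its CS results are medical history whenever they are received. A clinically significant worsening in a later sample is an AE.
- **SAP 4.3.6:** add that an abnormality whose only evidence is the baseline sample is not counted as a TEAE, so that the TEAE and baseline definitions agree.

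The cost is a few sentences in each document. No assessment is added and no clinical rule changes. Because the Visit 2 sample is defined as pre-dose, the rule does not need clock times for sampling or dosing, which the documents do not show are collected. For results already filed as AEs, the SAP rule calls for a check of laboratory AEs against the Visit 2 report, best done before unblinding.
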